10.4.2 Clinical Laboratory Parameters

Biochemistry and hematology data will be summarized separately for Parts A and B by treatment. Changes from baseline will be calculated.

Values for any biochemistry, hematology, and urinalysis values outside the clinical reference ranges will be flagged on the individual subject data listings.

AST, ALT, total and direct bilirubin will be summarized by treatment and timepoint. Changes from baseline will also be summarized.

The frequency of subjects who have a maximum ALT $>3x$ ULN for any post-dose timepoint will be presented by treatment group. Additionally, the frequency of subjects who have an ALT $> 3x$ ULN will also be presented for each assessment timepoint and treatment group. Similar tables shall also be presented for $>5x$ ULN and $>10x$ ULN. These frequency displays will also be provided for AST. The incidence of subjects who also have $>3x$ ULN increases in ALT and/or AST with $>2x$ ULN of total bilirubin will also be summarized by timepoint and treatment group.

A repeated measures ANCOVA will be used to compare the change from baseline in LDL cholesterol results between treatment groups on each day for Parts A and B separately. Dependent variables will be treatment, day, and the treatment by day interaction. The baseline variable will be used as a covariate.

Subject will be used as a random effect. The LS means for each treatment will be presented for each timepoint. Also, the difference from placebo, the 95% confidence interval of the difference from placebo, and p-value associated with the null-hypothesis of no difference will be for each day.

The SAS code will be similar to as shown below:

```
proc mixed data=xxx;
class subject day treatment;
model variable = baseline subject treatment day treatment*day;
repeated day / subject=subject type=csh;
lsmeans treatment*day / pdiff cl alpha=0.10;
ods output lsmeans=lsm;
ods output diffs=diff;
run;
```

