Study recruitment, progress and safety issues will be reviewed by the investigators, research nurse and research coordinators and communicated to the sponsor on a regular basis. The following will be reviewed: 1) subject enrollment, 2) preliminary findings that might affect the risk/benefit ratio or alter the procedures described in the protocol, 3) any clinically-significant out-of-range laboratory value and a course of action, and 4) any adverse or serious adverse events that might result from the research procedures.

The Safety Review Committee will review all available safety and PD data periodically during the study when approximately 33%, 66%, and 100% of the subjects in Part A have received a randomized treatment. After each safety data review, the Safety Review Committee will decide whether or not to continue with subject enrollment and dosing. Decisions to continue enrollment will be documented in the Safety Review Memo. REMD Biotherapeutics will issue a written notification of these decisions to investigators.

Determination of Adverse Event Severity and Relatedness

Adverse events will be coded per current MedDRA. Determination of the severity of adverse events will be consistent with Common Terminology Criteria for Adverse Events (CTCAE) V. 4.03. The relationship of an adverse event to treatment will be determined by the Investigator (see section 9: Reporting Procedures for All Adverse Events).

Dose Stopping Rules

Dosing will be stopped or modified if treatment-related AEs, changes in vital signs, ECG, or clinical laboratory results are observed and these changes pose a significant health risk, in the opinion of the Sponsor, Principal Investigator or Medical Monitor.

Medically significant AEs considered to be related to the investigational product and serious adverse events considered to be related to study procedures will be followed until resolved or considered stable.

A subject may be terminated at any point in time at the discretion of the Sponsor, Principal Investigator or Medical Monitor.

Stopping Rules for an Individual Subject:

At any time during the study, the subject must discontinue study drug treatment, if one of the following events occur:

- An increase of AST and/or ALT (> 3x ULN) are observed in the presence of increased (> 2x ULN) alkaline phosphatase and/or total bilirubin.
- A sustained AST or ALT increase, defined as three consecutive values of AST and/or ALT greater than 5x ULN within a period of 14 days.

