Fasting Plasma Glucose	2	15	30
Fasting Lipid Panel	5	9	45
Serum PK sample collection	4	6	24
Serum FSH levels (women only) ^Φ	5	1	5 ^Φ
HbA1c	6	4	24
Plasma Glucose via YSI	NA	NA	NA
MMTT (glucose & insulin)	40	2	80
GLP-1 (active & total), Glucagon, Plasma insulin and C-peptide	4	6	24
Anti-REMD-477 Ab sample collection *	10 (first) / 5	3	20
Exploratory biomarker collection	30	3	90
Serum Ketones & free fatty acids	1.5	15	22.5
TOTAL**			404.5 409.5^Φ

* First collection is 10 mL, subsequent collections are 5 mL.

** Volume to be collected over approximately 238 days.

Table 7-3: Total Blood Volume for samples collected under Protocol Amendment #2, for subjects participating in Part B

Procedure	Volume per Collection (mL)	Number of Collections	Total Volume (mL)
Safety (chemistry + hematology)	5	9	45
Fasting Plasma Glucose	2	15	30
Fasting Lipid Panel	5	9	45
Serum PK sample collection	4	6	24
Serum FSH levels (women only) ^Φ	5	1	5 ^Φ
HbA1c	6	5	30
GLP-1 (active & total), Glucagon, Plasma insulin and C-peptide	4	6	24
Anti-REMD-477 Ab sample collection *	10 (first) / 5	3	20
Exploratory biomarker collection	30	3	90
Serum Ketones & free fatty acids	1.5	15	22.5
Liver Injury Biomarkers	10	5	50
TOTAL**			380.5 385.5^Φ

* First collection is 10 mL, subsequent collections are 5 mL.

** Volume to be collected over approximately 224 days.

Laboratory Safety Tests

Blood and urine samples for laboratory safety tests (clinical chemistry, hematology, and urinalysis) will be collected according to the Schedule of Assessments ([Appendix A](#)).

The date and time of blood and urine collection will be recorded in the subject's source documentation. The tests will be analyzed using standard procedures. White blood cell differentials will be reported in absolute counts.

All laboratory tests must be reviewed by the Principal Investigator or qualified designee prior to the subject receiving each dose. Additional safety laboratory assessments may be performed if clinically indicated.

The following analytes will be tested:

Chemistry

Albumin	Blood urea nitrogen (BUN)
Calcium	Chloride
Glucose	Phosphorus
Potassium	Serum creatinine
Magnesium	Sodium
Bicarbonate	Uric acid
Aspartate aminotransferase (AST)	Alanine aminotransferase (ALT)
Cholesterol	Lactate dehydrogenase (LDH)
Alkaline phosphatase (ALP)	Total bilirubin
Total protein	Direct bilirubin
HDL, LDL, Triglycerides	Total globulin

Hematology

Red blood cells (RBC)
Hemoglobin (Hgb)
Hematocrit (Hct)
Mean corpuscular volume (MCV)

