15. APPENDICES

Appendix A. Schedule of Assessments – Part A

Study Period (or Dose #)	Screen	Lead-In		Dose 1		Dose 2	Dose 3	Dose 4	Dose 5	Dose 6	Dose 7	Dose 8
Study Week	≤ 42 days		Baseline Visit	1		2	3	4	5	6	7	8
Study Day		2 to 4 Weeks	Day -8/-7 to Day -2/-1	Pre-dose	1	8 ± 1	15 ± 1	22 ± 1	29 ± 1	36 ± 1	43 ± 1	50 ± 1
Informed consent	X											
Medical History ^a	X		X									
Physical examination	X		X						X			
Height (Screening only) & Body weight	X	X	X						X			
Urine pregnancy test (women); FSH ^g	X		X						X			
Urine drug/alcohol test	X		X						X			
12-lead ECG ^b	X		X						X			
Vitals (BP, RR, HR, T) ^c	X	X	X	X		X	X	X	X	X	X	X
Chemistry, Hematology, Lipid Panel, and Urinalysis	X		X			X	X		X		X	
Fasting (≥ 8-hr) plasma glucose ^e			X	X		X	X	X	X	X	X	X
Serum Ketones & Free Fatty Acids			X	X		X	X	X	X	X	X	X
Study Drug SC Administration					X	X	X	X	X	X	X	X
Seven-point blood glucose profile ^d		X						X				X
Unblinded Continuous Glucose Monitoring (CGM) ^h		X										
Ketone finger-stick ^j					X	X	X	X	X	X	X	X
Daily insulin usage dairy ⁱ		X			X	X	X	X	X			X
Hourly plasma glucose via YSI ^e			X ¹									
Mixed Meal Tolerance Test (MMTT) ^e			X									
Arginine Challenge Test ^e			X ¹									
HbA1c	X		X									
Insulin, C-peptide, GLP-1, and Glucagon ^{e,f}			X						X			
Serum PK sample collection ^f				X		X			X			
Anti-REMD-477 Ab sample collection ^f				X								
Exploratory biomarker collection				X								
QOL Questionnaires ^k			X									
Overnight Admission ^l			X									
Con-Med monitoring	X											
Adverse event monitoring												

Footnote Key:

- a. Medical history includes significant past medical events (e.g. prior hospitalizations or surgeries), a review of diabetes history and glycemic control, and any concurrent medical illnesses.
- b. After the Screening Visit, 12-lead ECG to be performed in triplicate, approximately 1 min apart. When ECG and blood sample collection occur at the same time, ECGs should be performed before blood samples are drawn.
- c. Vital signs include blood pressure, respiratory rate, heart rate, and oral temperature.
- d. Seven-point blood glucose profile will measure glucose by finger stick over three consecutive days before and 2 hours after each meal, and at bedtime.

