10.1.2 Repeat and Unscheduled Readings

Repeat readings occur when the original vital signs or ECG result requires confirmation. Repeat readings are labelled as 'Repeat' in the listings and replace the original readings in all summaries and changes from baseline presentations and calculations. Prior to dosing, all readings taken in addition to the original reading are defined as pre-dose repeats. Post-dose repeat readings are defined as readings collected within 15 minutes of the actual time of the original reading. Where results are taken in triplicate and repeated, the last three readings are used in all subsequent calculations.

All results not taken at a scheduled timepoint for other data types (eg, clinical laboratory parameters) are unscheduled. Unscheduled readings are labelled as 'Unscheduled' in the listings. Because unscheduled readings are not associated with any scheduled timepoint, they are excluded from all summaries (with the exception that they may be used as baseline, as stated in Section 10.1.1).

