10.4.4 Electrocardiogram

The ECG data will be obtained directly from the 12-lead ECG traces. These data include the QT interval calculated using the Bazett correction (QTcB), the QT interval calculated using the Fridericia correction (QTcF), the PR and QT intervals, the QRS duration, heart rate, and RR.

The ECG data will be summarized separately for Parts A and B by treatment, together with changes from baseline (see Section 10.1.1 for definitions of baseline). Figures of mean ECG data and mean change from baseline profiles will be presented separately for Parts A and B by treatment. The relationship between plasma concentrations of REMD-477 and changes from baseline in QTcF and QTcB will be explored graphically.

An outlier analysis will be performed including all individual post-dose QTcF and QTcB measurements (not the mean data), including all repeat and unscheduled readings. The frequency of subjects with a maximum increase from baseline in QTcB and QTcF intervals will be summarized for each treatment according to the following categories: >30 to 60 ms, >60, and \leq 30 ms. All incidences of >30 to \leq 60 ms, and >60 ms will be flagged on the listing. In addition, the frequency of subjects with QTcB and QTcF post-dose values will be summarized for each treatment, according to the following categories: >450 to 480, >480 to 500, >500, and \leq 450 ms. All incidences of >450 to 480, >480 to 500, and >500 ms will be flagged on the listing.

For Parts A and B separately the change from baseline of QT interval will be analyzed with a repeated measures ANCOVA. Dependent variables will be treatment, timepoint and the treatment by timepoint interaction. The change from baseline of the RR interval will serve as a covariate. Day is fitted as a repeated measure within subject. The estimated treatment means of the change from baseline of QT interval when change in RR interval equals zero will be presented for each timepoint. Also, the difference from placebo, the 95% CI of the difference from placebo, and p-value associated with the null-hypothesis of no difference will be presented for each timepoint.

An example of the SAS codes (abbreviated) is shown below:

```
proc mixed data=xxx;
  class subject day trtan;
```

```
model chg = chg_rr subject trtan day treatment*day;
repeated day / subject=subject type=csh;
lsmeans trtan*day / pdiff cl alpha=0.05;
estimate 'Est_CFB RR=0' intercept 1 chg_rr 0 trtan 1 0 avisit 1 0 0
trtan*avisit 1 0 0 0 0 0 /e;
...
run;
```

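### The maximum post-dose ALT and AST tables leave out unscheduled readings, so a peak seen only on a retest can be put in too low a category or missed

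*SAP*

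**What the plan says.** SAP 10.4.2 (Clinical Laboratory Parameters) plans subject counts by arm: "The frequency of subjects who have a maximum ALT $>3x$ ULN for any post-dose timepoint will be presented by treatment group". It adds the same display at >5x and >10x ULN, a version by assessment timepoint, and the same set for AST. A combined count is also planned: "ALT and/or AST with $>2x$ ULN of total bilirubin will also be summarized by timepoint and treatment group".

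SAP 10.1.2 treats any laboratory result taken off schedule as unscheduled. Of these it says "Because unscheduled readings are not associated with any scheduled timepoint, they are excluded from all summaries". The only exception is possible use as baseline.

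SAP 10.4.4 takes the other route for its QTc outlier analysis, which covers individual post-dose measurements "including all repeat and unscheduled readings".

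In the protocol, section 7 (Laboratory Safety Tests) provides that "Additional safety laboratory assessments may be performed if clinically indicated". Section 6 (Stopping Rules for an Individual Subject) stops dosing for a sustained rise, defined as "three consecutive values of AST and/or ALT greater than 5x ULN within a period of 14 days". Appendix A fixes the planned draws in the row "Chemistry, Hematology, Lipid Panel, and Urinalysis".

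**The concern.** A maximum-value table should show the worst value each subject reached. Transaminase elevation is the laboratory signal the protocol discusses when it justifies 35 mg and 70 mg (section 2, Dose Selection Rationale). An abnormal result is the usual reason for an extra draw, so retests tend to come from the subjects these tables are meant to count. Read as written, 10.1.2 removes those retests from the tables. The reported incidence above 3x, 5x or 10x ULN could then be too low, and more so in an arm where more subjects were retested. The combined ALT/AST and bilirubin count has the same weakness, because it is planned by timepoint only.

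**Working it through.** **Inputs.** Chemistry days come from Protocol Appendix A, Parts A and B. Visit windows are ±1 day up to Day 57 and ±2 days from Day 85. The stopping rule is in Protocol section 6. The plan is for 25 subjects per arm in each part.

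**Check of the schedule.** Screening + baseline + Days 8, 15, 29, 43, 57, 85, 162 = 2 + 7 = 9 draws. Protocol Tables 7-1 to 7-3 each give 9 chemistry and hematology collections, so the reading of the schedule agrees.

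**Gaps between scheduled post-dose draws.** 15 − 8 = 7; 29 − 15 = 14; 43 − 29 = 14; 57 − 43 = 14; 85 − 57 = 28; 162 − 85 = 77 days. Of the 11 dosing visits after Day 1, six have no scheduled chemistry (Days 22, 36, 50, 64, 71, 78). A recheck at any of those visits counts as unscheduled.

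**Can the sustained rule be met on scheduled draws alone?** Span of three successive draws = third day − first day. At the tightest windows, it is (third − window) − (first + window).

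| Draws | Nominal span (days) | Tightest span (days) |
|---|---|---|
| 8, 15, 29 | 21 | 28 − 9 = 19 |
| 15, 29, 43 | 28 | 42 − 16 = 26 |
| 29, 43, 57 | 28 | 56 − 30 = 26 |
| 43, 57, 85 | 42 | 83 − 44 = 39 |
| 57, 85, 162 | 105 | 160 − 58 = 102 |

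All exceed 14 days, so at least one of the three post-dose values is always unscheduled. In Part B the Day 1 pre-dose draw with Days 8 and 15 spans 14 days, but that draw precedes treatment and entry requires ALT and/or AST at or below 1.5x ULN at screening.

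**What the maximum tables then show.**

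| Scheduled post-dose values | Retest | Result under the SAP text |
|---|---|---|
| At least one >5x | >5x, not >10x | Counted correctly |
| At least one >5x, none >10x | >10x | In the >5x table, missing from >10x |
| At least one >3x, none >5x | >5x | In the >3x table, missing from >5x |
| None >3x | >3x | Missing from all the maximum tables |

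The last three rows are the loss.

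**Size per case.** One subject in an arm of 25 is 1/25 = 4 percentage points.

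**The case against.** The wording *any post-dose timepoint* could be read to take in retests. That does not sit well with 10.1.2, which bars unscheduled readings from all summaries, or with 10.4.4, which shows that the SAP states an exception when it wants one. The table shells that accompany the SAP (SAP section 4) were not available and might settle the matter.

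A reader might infer that a subject stopped under the sustained >5x rule drops out of the >5x table. The documents do not support that. One scheduled value above 5x is enough to be counted, and a run of retests will often follow an abnormal scheduled value. Such a subject should also surface elsewhere. Unscheduled values stay in the listings. Protocol section 10 lists early withdrawals with reasons and identifies adverse events leading to discontinuation. Meeting the rule also convenes the Safety Review Committee. This part of the objection stands. Adverse event tables are only partial cover for other subjects, since Protocol section 9 generally keeps abnormal values without clinical significance out of the adverse event record.

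Two further inferences fail. The isolated 18x ULN value in the type 2 diabetes study (Protocol section 2) is not an example of an off-schedule peak: the protocol says only that it was seen at one time-point. Nor can the loss be sized from the chance that a short rise falls between scheduled visits. That chance measures how often blood is drawn, and a rise never sampled is lost under any table rule.

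**Conclusion.** The point holds as a minor one. Under the SAP text, a subject whose highest post-dose ALT or AST was on a retest can be placed in too low a category, or left out of a maximum table when every scheduled value is at or below the cut-off. The combined count by timepoint can miss a case seen only on a retest in the same way.

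The number affected is not known, because the documents give no retest frequency; each case is worth 4 percentage points in an arm of 25. The conclusion assumes that 10.1.2 is applied as written and that the table shells do not override it. The primary analysis, the data collected and safety oversight during the trial are unaffected.

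A reader might also see gaps in the absence of counts between ULN and 3x ULN, and in the combined count using total bilirubin alone when the stopping rule applies where transaminase rises "are observed in the presence of increased (> 2x ULN) alkaline phosphatase and/or total bilirubin". Both are choices of display. The 3x and 5x cut-offs match the levels in the protocol's stopping rules, the SAP does not present the combined count as a tabulation of those rules, and the shells may add categories.

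**What to change.** In SAP 10.4.2:

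- Derive each subject's maximum post-dose ALT and AST from all post-dose values, unscheduled ones included, and state this as an exception to 10.1.2, in line with the QTc rule in 10.4.4.
- Add a subject-level count by arm of anyone with ALT and/or AST >3x ULN with total bilirubin >2x ULN at any post-dose draw, scheduled or not.
- Keep the tables by timepoint on scheduled visits.
- Show the number of unscheduled draws per arm beside the maximum table.

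The cost is a few lines of SAP text and a small programming change; no new data are needed. Reported incidence may be slightly higher, and subjects retested more often get more chances to reach a higher category. The count of unscheduled draws lets the reader judge whether that differs between arms.

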10.4.3 Vital Signs

The vital signs data (blood pressure, respiratory rate, pulse rate and body temperature) will be summarized separately for Parts A and B by treatment, together with changes from baseline (see Section 10.1.1 for definitions of baseline). Figures of mean vital signs and its changes from baseline will be presented by treatment.

A repeated measures ANCOVA will be used to compare the change from baseline in pulse rate and systolic and diastolic blood pressure results between treatment groups on each day for Parts A and B separately. Dependent variables will be treatment, day, and the treatment by day interaction. The baseline variable will be used as a covariate.

Subject will be used as a random effect. The LS means for each treatment will be presented for each timepoint. Also, the difference from placebo, the 95% confidence interval of the difference

from placebo, and p-value associated with the null-hypothesis of no difference will be for each day.

The SAS code will be similar to as shown below:

```
proc mixed data=xxx;
  class subject day treatment;
  model variable = baseline subject treatment day treatment*day;
  repeated day / subject=subject type=csh;
  lsmeans treatment*day / pdiff cl alpha=0.10;
  ods output lsmeans=lsm;
  ods output diffs=diff;
  run;
```

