10.1.1 Definition of Baseline and Change from Baseline

Unless otherwise stated, the baseline for each parameter is defined as the last value measured prior to first dosing, including repeat (vital signs and electrocardiograms [ECGs]) and unscheduled (clinical laboratory parameters) readings (see Section 10.1.2 for definitions of repeat and unscheduled readings). For ECGs taken in triplicate, baseline will be the mean of the last three values taken prior to first dosing.

Mean change from baseline is the mean of all individual subjects' change from baseline values. Each individual change from baseline will be calculated by subtracting the individual subject's baseline value from the value at the timepoint. The individual subject's change from baseline values will be used to calculate the mean change from baseline using a SAS procedure such as Proc Univariate.

Mean percent change from baseline is the mean of all individual subjects' percent change from baseline values. Each percent change from baseline will be calculated by subtracting the individual subject's baseline value from the value at the desired timepoint and then dividing this calculated value by the individual subject's baseline value and multiplying by 100. These individual subjects' percent changes from baseline values will be used to calculate the mean percent change from baseline using a SAS procedure such as Proc Univariate.

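### Pulse and blood pressure are analysed against one last pre-dose reading; averaging the readings from the Lead-In on, in both change score and covariate, would give modestly tighter placebo comparisons

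*SAP*

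**What the plan says.** SAP 10.4.3 plans a model for three vital signs: "A repeated measures ANCOVA will be used to compare the change from baseline in pulse rate and systolic and diastolic blood pressure results", by day and separately for Parts A and B. It refers to 10.1.1 for baseline and adds: "The baseline variable will be used as a covariate".

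In SAP 10.1.1, unless another section states otherwise, "the baseline for each parameter is defined as the last value measured prior to first dosing". Under 10.1.2, repeat readings "replace the original readings in all summaries and changes from baseline presentations and calculations". A repeat therefore replaces a reading and is not averaged with it, so each subject contributes one baseline reading. Averaging is specified in 10.1.1 only for triplicate ECGs, where "baseline will be the mean of the last three values taken prior to first dosing".

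In Protocol Appendix A, the Part A row "Vitals (BP, RR, HR, T) ^c" is marked at Screening, Lead-In, Baseline Visit and Day 1 pre-dose. The same row for Part B is marked at Screening, Lead-In and the Day 1 baseline/pre-dose column. No section of either document uses the readings before the last one in the model.

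**The concern.** One pulse or blood pressure reading is a noisy measure of a subject's usual level. A noisier covariate explains less of the post-dose variation, so the difference from placebo has a larger standard error than the collected data permit. Planned size is 25 per group, and the Parts are analysed separately. Precision therefore limits how small a pulse or blood pressure effect can be excluded. The protocol pays attention to blood pressure for this drug: its summary of study R477-201 comments on the absence of an increase.

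**Working it through.** **The plan's own figures.** The documents state no SD, correlation, interval width or power for pulse or blood pressure, so there is no vital-sign figure to reproduce. The only design figure concerns daily insulin use: 2 × (1.960 + 0.842)² × (0.36/0.30)² = 22.6, so 23 per group against the stated 22. It does not bear on this point.

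**Inputs from the documents.** 25 per group in each Part. From the Lead-In on, k = 3 scheduled pre-dose readings in Part A and k = 2 in Part B.

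**Assumed inputs (not in the documents).** Between-subject and visit-to-visit SDs: SBP 12–14 and 7–10 mmHg; DBP 8 and 5–6 mmHg; pulse 8–10 and 6–8 bpm.

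**Step 1: constant correlation over time**, as in the SAP's covariance structure. Let b be the between-subject variance and w the visit-to-visit variance. The residual variance at a visit is:

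- last reading as baseline: V1 = b + w − b²/(b + w)
- mean of k readings in both change and covariate: Vk = b + w − b²/(b + w/k)
- mean of k readings as covariate only, change still taken from the last reading: Vc = 2w − (w/k)²/(b + w/k)

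The third form differs because ANCOVA on change is equivalent to ANCOVA on the post-dose value only when the covariate is the value that was subtracted. Otherwise the last reading's noise stays in the outcome.

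For SBP with SDs 12 and 8, b = 144 and w = 64:

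- V1 = 208 − 20736/208 = 108.3
- k = 3: Vk = 208 − 20736/165.33 = 82.6, ratio 0.762
- k = 2: Vk = 208 − 20736/176 = 90.2, ratio 0.833
- k = 3, covariate only: Vc = 128 − 455.1/165.33 = 125.2, ratio 1.156

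With SE = √(2V/25):

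| Baseline (SBP 12/8, k = 3) | SE, mmHg | Against current plan |
|---|---|---|
| Last reading (current) | 2.94 | – |
| Mean in change and covariate | 2.57 | 13% smaller |
| Mean in covariate only | 3.17 | 7.5% larger |

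A simulation of 4000 trials with 25 per arm gave 2.95, 2.57 and 3.17.

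Over the whole assumed SD range, the SE cut from averaging in both places is 8.7–14.8% for k = 3 and 5.7–10.4% for k = 2. Changing the covariate alone raises the SE by 3.9–13.0%.

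**Step 2: correlation that decays with time.** Take the correlation between two readings as R·exp(−lag/τ), with assumed R of 0.5–0.7 and τ of 100–400 days. Assumed reading days are −21, −4 and 1, or −36, −8 and 1, in Part A, and −7 and 1, or −14 and 1, in Part B. Averaging in both places then cuts the SE by 2.9–10.5% at Day 8 and 0.4–5.4% at Day 85. It narrowed the interval in every case tried.

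**Step 3: the printed code.** The text of 10.4.3 treats subject as random and asks for 95% intervals. The code lists subject as a class effect in the MODEL statement and sets alpha=0.10. A rank check of that design shows that neither the baseline slope nor the treatment-by-day difference from placebo is estimable; without subject in MODEL, the difference is estimable. The 90% level makes intervals about 16% narrower than 95% ones (1.645/1.960 = 0.839). Steps 1 and 2 therefore apply to the model in the text, not to the code as printed.

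**The case against.** The strongest case is that this is a preference. The last pre-dose value is conventional and unbiased, and the protocol says the Day 1 pre-dose measurements serve as baseline in Part B. These are safety comparisons with no stated power, margin or decision rule. All of that stands, and it limits the point to precision.

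The size rests on SDs and correlations that the documents do not supply. This also stands: the percentages are conditional, and by Day 85 the gain may be close to nothing.

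The ECG comparison carries little weight. Those triplicates are taken about a minute apart at one visit, which differs from pooling visits over weeks. A closer precedent is SAP 10.3.4.7, where the ketone and free fatty acid baseline for early Part A subjects averages the Lead-In (OBV) value and Day 1 pre-dose.

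Three stronger readings are tempting. A reader might infer that the single reading biases the comparison or is an error; nothing in the documents supports that. A reader might take a percentage loss as established by the data; it is not, because every variance input is assumed. A reader might want every pre-dose reading used, including Screening. That reading can be up to 42 days before the Lead-In begins, and with decaying correlation a plain mean including it changed interval width at Day 8 by anything from a loss of about 1% to a gain of about 12%.

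**Conclusion.** The point holds as a small, optional gain in precision from data already collected. It is not a bias, an error or a threat to any stated conclusion. Under the assumed SDs and constant correlation, the standard error of the placebo difference would fall by about 9–15% in Part A and 6–10% in Part B. Under the assumed decay, it would fall by about 3–10% at Day 8 and 0.5–5% at Day 85. The gain requires the averaged value in both the change and the covariate, or the post-dose value as outcome. It also requires the model in the text. The conflicts between text and code in 10.4.3 matter at least as much as the choice of baseline.

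**What to change.** Add to SAP 10.4.3: for the ANCOVA of pulse, SBP and DBP, baseline is the mean of all scheduled pre-dose readings from the Lead-In on, one value per visit with a repeat replacing its original; this mean is used both to compute the change from baseline and as the covariate. Equivalently, analyse the post-dose value with this mean as covariate. Do not change the covariate alone.

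In the same edit, make text and code agree: handle subject as the text describes instead of as a MODEL effect, and set one interval level. The protocol's vital-signs analysis also asks for 95%.

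The cost is one sentence, one derived variable, a code correction and an entry in SAP section 12. No new data are needed. The descriptive tables may keep the last value. The small downside is that the model's baseline then differs from 10.1.1, from those tables and, in Part B, from the protocol's Day 1 baseline. All the readings precede first dosing, so averaging them adds no bias.
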